The study will enroll approximately 330 patients at approximately 110 global sites.

At Weeks 1, 5, 9, 13, and 16 the primary breast tumor and axillary lymph nodes will be assessed by clinical breast examination (palpation and caliper measurement). Suspicion of progression based on clinical exam at any time should be further evaluated (Figure 6).

[figure not shown]
At Week 9, a breast ultrasound will be performed to ensure that there is no progressive disease and for the purpose of surgery planning. Suspicion of progressive disease on breast ultrasound should be confirmed by investigator-assessed breast MRI. Patients with primary disease not evaluable by ultrasound at baseline should be assessed by MRI at Week 9. Suspected progression in nodes should also be confirmed by fine needle aspiration (FNA) if these nodes had not been previously shown to be cytologically positive for cancer. Patients with progressive disease (as defined by modified RECIST, [Appendix 3](#)), can either proceed directly to surgery or be taken off of the study, according to the investigator's decision. If the patient goes off-study, every reasonable effort should be made to obtain a new biopsy prior to beginning another systemic treatment.

From Week 13, the patient will visit with the surgeon. The purpose of this visit is two-fold: tentative planning of the type of breast surgery to be performed (breast conservative vs. mastectomy) and scheduling the date for definitive surgery.

During Week 16, breast MRI will be done for the purpose of primary endpoint analysis. Clinical breast exam, breast ultrasound, and mammography will also be conducted prior to surgery for the purpose of the secondary endpoint analysis.

Blood sample for exploratory endpoint analysis will be collected at screening, at Week 3, and prior to surgery.

Figure 6 Schematic Representing Confirmation of Progression

FNA=fine needle aspiration; MRI =magnetic resonance imaging; PD=progressive disease.

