3.3.4.3 Rationale for Using the Preoperative Endocrine Prognostic Index Score

In addition to Ki67, pathologic tumor size (T1 or T2 versus T3 or T4), node status (positive or negative), and the ER status (positive Allred score 3–8 versus negative Allred score 0–2) of the surgery specimen were also determined to have independent prognostic value for relapse and death after relapse in the P024 trial (Ellis et al. 2008 [22]). A PEPI score, prognostic for RFS, which weighs each of these factors according to their associated hazard ratios, was developed and subsequently validated in an independent data set from the IMPACT trial (Ellis et al. 2008). No relapses were recorded in either trial in patients with tumors classified as T1N0 and with a PEPI score of 0 (residual tumor with a Ki67 level $\leq 2.7\%$, and with maintained ER expression) or in the rare patient with a pCR.

In this trial, the PEPI score will be assessed centrally.

3.3.4.4 Rationale for Assessing ORR by Clinical Breast Exam (Palpation), Mammography, and Breast Ultrasound

Objective overall response rate will also be assessed by clinical breast exam, mammography, and breast ultrasound during screening and prior to surgery. These data will allow for more direct comparison of results to other neoadjuvant trials with endocrine therapy as described in [Section 3.3.3](#). The concurrent acquisition of ORR data with these techniques, in addition to MRI-based measures, will also provide valuable comparative information on these methods, which will be important for both future neoadjuvant studies and GDC-0032 clinical development.

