4.1.1 Inclusion Criteria

Patients must meet the following criteria for study entry:

- Signed Informed Consent Form (ICF) prior to any study-specific procedure
- Female patients
- Postmenopausal status and age ≥ 18 years. Postmenopausal status is defined as follows:
 - Age ≥ 60 years or
 - Age < 60 years and 12 months of amenorrhea plus follicle stimulating hormone (FSH) and plasma estradiol levels within postmenopausal range by local laboratory assessment or
 - Prior bilateral oophorectomy (≥ 28 days prior to Day 1 of treatment)
- Histologically confirmed invasive breast carcinoma, with all of the following characteristics:
 - Primary tumor ≥ 2 cm in largest diameter (cT1-3) by MRI. In the case of a multifocal tumor (defined as the presence of two or more foci of cancer within the same breast quadrant), the largest lesion must be ≥ 2 cm and designated as the “target” lesion for all subsequent tumor evaluations.
 - Stage I to operable Stage III breast cancer
 - Documentation confirming the absence of distant metastasis (M0) as determined by institutional practice (in patients where there may be a reasonable suspicion of advanced disease e.g., large tumors, clinically positive axillary lymph nodes, signs and symptoms).
- ER-positive and HER2-negative breast cancer, as per local laboratory or regional definition
- Breast cancer eligible for primary surgery
- Tumor tissue from FFPE core biopsy of breast primary tumor that is confirmed as evaluable for *PIK3CA* mutation status by central histopathology laboratory
- Eastern Cooperative Oncology Group (ECOG) performance status of 0 or 1
- Fasting glucose ≤ 125 mg/dL
- Adequate hematological, renal, and hepatic function, as follows:
 - Absolute neutrophil count $\geq 1500/\mu\text{L}$
 - Platelets count $\geq 100,000/\mu\text{L}$

- Hemoglobin ≥ 9 g/dL
- Serum bilirubin $\leq 1.5 \times$ the upper limit of normal (ULN)
- Patients with known Gilbert's disease who have serum bilirubin $\leq 3 \times$ ULN may be enrolled
- Aspartate aminotransferase (AST), alanine transaminase (ALT), alkaline phosphatase $\leq 1.5 \times$ ULN
- Serum creatinine $\leq 1.5 \times$ ULN or creatinine clearance ≥ 50 mL/min on the basis of the Cockcroft–Gault glomerular filtration rate estimation:

$$\frac{(140 - \text{age}) \times (\text{weight in kg}) \times (0.85)}{72 \times (\text{serum creatinine in mg/dL})}$$

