6.4 EFFICACY ANALYSES

The primary and secondary efficacy analyses will include the ITT population; that is, all randomized patients will be included in the analyses, with patients grouped according to the treatment assigned at randomization.

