6.4.2 Secondary Efficacy Endpoints

The secondary efficacy endpoints for this study are as follows:

- Tumor ORR after completion of study treatment, assessed by modified RECIST criteria by breast MRI in *PIK3CA* WT patients.
- Rate of pCR in breast and axilla (total pCR) after completion of study drug in *PIK3CA* WT patients.

These endpoint measures will be summarized by treatment arm and will be analyzed analogue to the primary efficacy endpoint.

The following secondary efficacy endpoints will be performed in all enrolled patients and separated by *PIK3CA* mutation status:

- ORR by clinical breast examination, mammography, and breast ultrasound
- Ki67 values at baseline, Week 3, and surgery (centrally assessed)
- Change in Ki67 from baseline to Week 3; baseline to surgery, and Week 3 to surgery (centrally assessed)
- PEPI score (centrally assessed)
- Change in enhancing tumor volume from baseline to surgery as measured by breast MRI

- Evaluation of different definitions of pCR including the following: a) ypT0, ypN0, and b) ypT0/is, ypNX (breast pCR)

These endpoint measures will be summarized by treatment arm and will be compared between the two treatment arms within each population based on appropriate statistical analyses: ORR will be compared using a Cochrane Mantel-Haenszel test, stratified by tumor size and nodal status; PEPI, Ki67, and tumor volume change will be compared by regression analyses, adjusted for tumor size and nodal status. All secondary endpoints will be tested at a two-sided type I error of 5%.

More details of the analyses will be provided in the Statistical Analysis Plan (SAP).

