Appendix 2 Schedule of Pharmacokinetic Assessments

Visit	Timepoint	PK Assessments
Day 1	3 hours post (± 60 min) letrozole and GDC-0032/placebo administration	Letrozole PK
		GDC-0032 PK
Day 15 (+ 2 days)	0–4 hours prior to letrozole and GDC-0032/placebo administration	Letrozole PK
		GDC-0032 PK
	3 hours (± 60 min) post letrozole and GDC-0032/placebo administration ECG before PK	Letrozole PK
		GDC-0032 PK
Day 57 (+/- 2 days)	3 hours post (± 60 min) letrozole and GDC-0032/placebo administration	Letrozole PK GDC-0032 PK

ECG=electrocardiogram; min=minutes; PK=pharmacokinetics.

Record exact time of dose administration and sample collection.

Appendix 3

Modified Response Evaluation Criteria in Solid Tumors: Assessment of Response of Neoadjuvant Therapy in Early Breast Cancer

Conventional response criteria may not be ideal for the assessment of response in the setting of neoadjuvant therapy in early breast cancer. Therefore, RECIST 1.1 criteria have been modified to specifically address assessment of primary breast lesions along with axillary lymph node disease, using a range of breast imaging modalities. Selected sections from the Response Evaluation Criteria in Solid Tumors (RECIST), Version 1.1¹ are presented below, with modifications and the addition of explanatory text as needed for clarity. For detailed information on the read methodology including how imaging data should be processed prior to reads, please refer to the Study Imaging Charter.

	RECIST v1.1	Modified RECIST Early Breast Cancer Neoadjuvant Therapy
Modalities	CT as primary modality, ultrasound not recommended	No CT; primary assessments by MRI; also assessments by ultrasound, mammography, and clinical exam
Lymph nodes	May be considered target lesions based on size criteria (≥ 15 mm in SAD)	Only axillary lymph nodes assessed; nodes that are considered abnormal on imaging (based on morphological factors including, but not limited to SAD) to be followed as non-target lesions
Possibility of having only non-target disease	Allowed	Not allowed; primary breast lesions must be measurable by MRI and/or ultrasound

CT = computed tomography; MRI = magnetic resonance imaging; SAD = short axis dimension.

BASELINE DOCUMENTATION OF TARGET AND NON-TARGET LESIONS

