- Partial response (PR): at least a 30% decrease in the sum of diameters of target lesions, taking as reference the baseline sum of diameters
- Progressive disease (PD): at least a 20% increase in the sum of diameters of target lesions, taking as reference the smallest sum on study (nadir), including baseline

In addition to the relative increase of 20%, the sum must also demonstrate an absolute increase of at least 5 mm.

The appearance of one or more new lesions is also considered progression.

- Stable disease (SD): neither sufficient shrinkage to qualify for PR nor sufficient increase to qualify for PD, taking as reference the smallest sum on study

Special Notes on the Assessment of Target Lesions

Target Lesions That Become Too Small to Measure. While on study, all lesions recorded at baseline should have their actual measurements recorded at each subsequent evaluation, even when very small (e.g., 2 mm). However, sometimes lesions that are recorded as target lesions at baseline become so faint on imaging that the radiologist may not feel comfortable assigning an exact measure and may report them as being too small to measure. When this occurs, it is important that a value be recorded on the CRF as follows:

- If it is the opinion of the radiologist that the lesion has likely disappeared, the measurement should be recorded as 0 mm.
- If the lesion is believed to be present and is faintly seen but too small to accurately measure, BML (below measurable limit) should be indicated.

To reiterate, however, if the radiologist is able to provide an actual measure, that should be recorded, and, in that case, BML should not be ticked.

Appendix 3

Modified Response Evaluation Criteria in Solid Tumors: Assessment of Response of Neoadjuvant Therapy in Early Breast Cancer (cont.)

Lesions That Split or Coalesce on Treatment. When non-nodal lesions fragment, the longest diameters of the fragmented portions should be added together to calculate the target lesion sum. Similarly, as lesions coalesce, a plane between them may be maintained that would aid in obtaining maximal diameter measurements of each individual lesion. If the lesions have truly coalesced such that they are no longer separable, the vector of the longest diameter for the coalesced lesion should be recorded.

Evaluation of Non-Target Lesions

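### ORR by ultrasound, mammography and palpation is analysed in all randomised patients, including any with no baseline target lesion by that method, which shrinks the absolute difference and costs some power (minor)

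*Protocol*

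**What the plan says.** - **Analysis set.** Section 6.4: "The primary and secondary efficacy analyses will include the ITT population; that is, all randomized patients will be included in the analyses". Section 6.4.2 lists "ORR by clinical breast examination, mammography, and breast ultrasound" among the secondary endpoints, to be analysed overall and by PIK3CA status, each at 5% two-sided.
- **Entry.** The size criterion in section 4.1.1 is "Primary tumor ≥ 2 cm in largest diameter (cT1-3) by MRI". The comparison table in Appendix 3, on having only non-target disease, reads "Not allowed; primary breast lesions must be measurable by MRI and/or ultrasound". No criterion asks for a lesion measurable on mammography or by palpation.
- **Expected gaps.** Section 3.1: "Patients with primary disease not evaluable by ultrasound at baseline should be assessed by MRI at Week 9". Section 4.5.7 and the MRI footnote of Appendix 1 carry similar provisions.
- **Response.** Section 3.4.1.2 applies modified RECIST to these three methods. In Appendix 3, complete response is the disappearance of target lesions and partial response is "at least a 30% decrease in the sum of diameters of target lesions, taking as reference the baseline sum of diameters". The same technique must be used at baseline and follow-up.
- **Missing outcomes.** The only non-responder rule, in section 6.4.1, covers patients who leave the study early.

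**The concern.** Both response categories need a target lesion that the method in question saw at baseline. If a tumour qualified on MRI but cannot be measured by, say, mammography, the patient has no baseline sum on mammography and cannot reach either category by that method, whatever the drug does. The all-randomised denominator keeps her in.

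At stake is the sensitivity of three secondary arm comparisons: the absolute difference shrinks and power falls for a reason unrelated to treatment. Elsewhere the protocol does tie the analysis set to having a usable baseline (Ki67 in section 6.6, patient-reported outcomes in section 6.8). It gives no such set for these three ORRs, which depend on baseline just as much.

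**Working it through.** **The plan's own figure.** The protocol states no sample size or power for these methods. Its nearest figure is 108 evaluable PIK3CA-mutant patients for MRI ORR, 40% vs 64%, at 16% two-sided and 80% power with a 40:60 split (section 6.1). The continuity-corrected two-proportion formula gives 43 + 65 = 108, which reproduces it. That figure is not touched by this point.

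**Inputs**
- N = 330, 1:1 allocation, 5% two-sided (sections 6.1, 4.2.2, 6.4.2).
- Letrozole ORR from the letrozole-versus-tamoxifen trial cited in section 3.3.3: ultrasound 35%, mammography 34%, palpation 55%.
- Share without a baseline target lesion by the method, u: not in the documents. Assumed 10% to 30%.
- Effect among measurable patients: not in the documents for these methods. Assumed 15 points.

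**Dilution.** With every randomised patient in the denominator, the rate in each arm is p(1−u), so the difference is d(1−u). The ratio p2(1−u)/p1(1−u) = p2/p1 does not change.

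**Power.** Unstratified normal approximation with n per arm: power = Φ{[d√n − 1.96√(2p̄(1−p̄))] / √(p1(1−p1) + p2(1−p2))}. The all-randomised analysis uses the diluted rates with n = 165. The measurable-only analysis uses the undiluted rates with n = 165(1−u).

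Ultrasound at u = 10%:
- All randomised: rates 0.315 and 0.450, p̄ = 0.3825. (0.135 × 12.845 − 1.96 × 0.6873)/0.6806 = 0.569, so power is 71.5%.
- Measurable only: rates 0.35 and 0.50, n = 148.5. (0.15 × 12.186 − 1.96 × 0.6991)/0.6910 = 0.662, so power is 74.6%.

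| Method | u | All-randomised rates | Difference (points) | Power, all randomised | Power, measurable only |
|---|---|---|---|---|---|
| Ultrasound | 0 | 35.0% vs 50.0% | 15.0 | 79.0% | 79.0% |
| | 10% | 31.5% vs 45.0% | 13.5 | 71.5% | 74.6% |
| | 20% | 28.0% vs 40.0% | 12.0 | 63.4% | 69.5% |
| | 30% | 24.5% vs 35.0% | 10.5 | 55.1% | 63.7% |
| Mammography | 10% | 30.6% vs 44.1% | 13.5 | 71.9% | 74.9% |
| | 20% | 27.2% vs 39.2% | 12.0 | 64.0% | 69.8% |
| Palpation | 10% | 49.5% vs 63.0% | 13.5 | 69.7% | 76.4% |
| | 20% | 44.0% vs 56.0% | 12.0 | 58.8% | 71.4% |

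The gap in power is 3.0 to 6.7 points at u = 10% and 5.8 to 12.6 points at u = 20%. The measurable-only analysis has the higher power in every row with u above zero, despite its smaller n.

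**Type I error.** Measurability at baseline precedes treatment, so randomisation balances it in expectation. With no treatment effect both arms have the same diluted rate, and the test keeps its level.

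**The case against.** The strongest objection concerns comparability. Section 3.3.4.4 says of these endpoints that "These data will allow for more direct comparison of results to other neoadjuvant trials with endocrine therapy". A reader might infer that the all-randomised denominator distorts that comparison. The protocol's own account does not support this. Section 3.3.3 gives the palpation response of the letrozole-versus-tamoxifen trial in the ITT population, and likewise the caliper and ultrasound response of the anastrozole/tamoxifen trial. For those comparators an all-randomised rate is the like-for-like figure, and replacing it outright would move this trial away from them. This part of the objection stands, and it is why the all-randomised rate should still be reported.

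Nor can one say that per-method subsets would make the methods easier to compare with each other. With all randomised patients, every method is rated on the same people. With subsets, three partly different groups are compared. That stands too, and limits what the fix can claim.

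Third, the protocol nowhere says that a patient unmeasurable at baseline counts as a non-responder. That status follows from the denominator, not from a stated rule. Section 6.4.2 leaves further detail to the SAP, which is not among the documents here and may define a set. But section 6.4 states the analysis set for secondary endpoints without exception, so a SAP that used another set as its main analysis would depart from the protocol.

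Finally, u is nowhere given. Baseline gaps are acknowledged only for ultrasound; for mammography and palpation they follow from the absence of an entry requirement. With tumours of at least 2 cm, u may be small.

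**Conclusion.** The point holds as a minor one. As written, the protocol fixes a denominator for three secondary ORRs that can include patients who cannot respond by the method, and this multiplies both rates and the absolute difference by (1−u). That factor is exact if such patients are counted as non-responders. Its size here is not known: under the assumed 15-point effect it means 13.5 points at u = 10% and 12 at u = 20%, with about 3 to 7 and 6 to 13 points less power than a measurable-only analysis at N = 330.

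A reader might also infer a biased arm comparison, an inflated type I error or a threat to the primary result. None of these follows. The expected response ratio is unchanged, the test keeps its level, and the MRI co-primary endpoint, whose entry criterion is itself by MRI, is unaffected.

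**What to change.** In section 6.4.2, for ORR by ultrasound, mammography and clinical examination, compare arms in randomised patients with a target lesion measurable by that method at baseline. Group patients by assigned arm and count post-baseline missing as non-response. Define the set from the screening measurements, because Appendix 1 places randomisation within screening. Nothing after randomisation then decides who is in.

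Report the all-randomised rate alongside, for comparison with the ITT rates of the cited trials, and give the number excluded by arm for each method. Leave the MRI co-primary analysis as it is.

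The cost is a sentence or two in section 6.4.2. No new data field is needed: section 4.5.7 already has measurable disease documented at screening and the caliper, mammographic and sonographic measurements entered in the eCRF. The downside is that each method has its own, smaller denominator, so the report should say that these rates are not to be compared directly between methods.

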6.4.1 Primary Efficacy Endpoint

The co-primary efficacy endpoints are (1) tumor ORR, assessed by modified RECIST criteria by breast MRI and (2) the rate of pCR in breast and axilla (total pCR) after completion of study drug.

The tumor ORR will be calculated by treatment arm in all enrolled population and in *PIK3CA* MT population. Within each population, the ORR for the two treatment arms will be compared at a two-sided alpha of 16% using a Cochran Mantel-Haenszel test, stratified by tumor size and nodal status. The pCR rate will also be calculated and compared at a two-sided alpha of 4% based on the same analytical approach as ORR. The two alpha values account for a family-wise type I error rate of 20%. Patients with early study termination and hence missing efficacy outcome will be considered as non-responders.

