6.1 DETERMINATION OF SAMPLE SIZE

This study is designed for testing the effect of GDC-0032 on the two co-primary endpoints in all enrolled patients and in the *PIK3CA* MT patients and plans to enroll 330 patients in total. Assuming the *PIK3CA* mutation status will not be available (unknown) for approximately 10% of the patients and the prevalence of *PIK3CA* mutant is 40%, there will be approximately 120 patients in the *PIK3CA* MT cohort.

Given that the *PIK3CA* mutation status is not a stratification factor for randomization, there might be a possible imbalance between treatment arms within the *PIK3CA* MT cohort, which may reduce the statistical power in this cohort. To ensure the study provides sufficient statistical power even when the treatment assignment is imbalanced, the sample size was calculated based on a conservative scenario by assuming that the treatment assignment imbalance in *PIK3CA* MT is 40% vs. 60%. The sample size was calculated based on a chi²-test using continuity correction (Ury and Fleiss 1980 [63]).

To control an overall, two-sided, family-wise error rate under 20%, we use a two-sided significance level of 16% and 4% for the co-primary endpoints MRI ORR, and pCR, respectively.

Assuming 10% of the patients are unevaluable for the MRI ORR, approximately 300 enrolled patients and 108 patients in the *PIK3CA* MT cohort will be evaluable for analyses. This sample size allows us to detect an absolute percentage increase of 24% in MRI ORR rate in the GDC-0032 plus letrozole arm (64%) versus the letrozole-only arm (40%; Smith et al. 2005 [59]; Ellis and Ma 2007 [21]) in the *PIK3CA* MT cohort at 80% power and 16% two-sided significance level. The minimal detectable difference for ORR is approximately 15%.

Assuming that all patients are evaluable for pCR (i.e., approximately 330 enrolled patients and 120 in the *PIK3CA* MT cohort), this sample size provides 80% power to detect an absolute percentage increase of 18% in pCR in the GDC-0032 plus letrozole arm (19%) versus the letrozole-only arm (1%, Smith et al. 2005 [59]; Ellis and Ma 2007 [21]) in the *PIK3CA* MT cohort at the 4% two-sided significance level. The minimal detectable difference for pCR rate is approximately 13%.

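### Each co-primary endpoint is tested at its full alpha in two populations, so the stated 20% family-wise error rate is really about 30%

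*Protocol*

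**What the plan says.** Section 6.1 says the study is designed to test both co-primary endpoints in all enrolled patients and in PIK3CA mutant patients. The objectives (2.1) and the outcome measures (3.4.1.1) define each endpoint in both populations.

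Section 6.1 sets the error budget: "To control an overall, two-sided, family-wise error rate under 20%, we use a two-sided significance level of 16% and 4" percent for MRI ORR and pCR respectively. Section 6.4.1 then fixes the tests:

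- On the populations: "The tumor ORR will be calculated by treatment arm in all enrolled population and in" the PIK3CA mutant population.
- On the ORR test: "Within each population, the ORR for the two treatment arms will be compared at a two-sided alpha of 16" percent, by a stratified Cochran-Mantel-Haenszel test.
- On the pCR test: "The pCR rate will also be calculated and compared at a two-sided alpha of 4% based on the same analytical approach as ORR".
- On the error rate that these levels are meant to secure: "The two alpha values account for a family-wise type I error rate of 20" percent.

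The synopsis repeats the error budget. Nothing in the protocol orders the two populations, divides alpha between them, or requires success in both.

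**The concern.** The 16%/4% split divides the error budget between endpoints. It leaves nothing to divide between populations, yet each endpoint is tested twice at its full level. Four tests at 16%, 16%, 4% and 4% are planned against a budget that pays for two.

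As written, a significant result on either endpoint in either population could be presented as a primary finding from a procedure with a 20% family-wise error rate. The procedure does not have that property.

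**Working it through.** **Inputs from Section 6.1.** For ORR, "approximately 300 enrolled patients and 108 patients in the" mutant cohort are evaluable. For pCR it is "approximately 330 enrolled patients and 120 in the" mutant cohort. Assumed rates are 40% versus 64% (ORR) and 1% versus 19% (pCR), with 80% power, 40:60 allocation in the mutant cohort, and a continuity-corrected chi-square test for sample size. The protocol gives no correlation between the ORR and pCR test statistics. I assume a range of 0 to 0.9.

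**1. The plan's own figure.** One test per endpoint gives 0.16 + 0.04 = 0.20 as the Bonferroni bound, or 1 − 0.84 × 0.96 = 0.194 if the endpoints are independent. So 20% is right for two tests.

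**2. Where the alpha is spent.** With the protocol's formula (continuity correction, 40:60 allocation), ORR at 16% needs 108 evaluable mutant patients, exactly as stated. pCR at 4% needs 123, against a stated 120. The full 16% and 4% therefore go to the mutant cohort alone.

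**3. Correlation of the nested tests.** Under the null, the statistics for a subgroup and for the whole correlate at √(n_MT / n_all):

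- ORR: √(108/300) = 0.600
- pCR: √(120/330) = 0.603

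**4. Each pair.** P(at least one rejection) = 1 − P(|Z₁| ≤ c, |Z₂| ≤ c) for a bivariate normal, where c = z(0.92) for ORR and z(0.98) for pCR.

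- ORR pair: 26.2%, not 16%
- pCR pair: 7.1%, not 4%

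**5. All four tests** (multivariate normal simulation, 8 million draws):

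| Between-endpoint correlation | Four tests as written | Two tests (one per endpoint) |
|---|---|---|
| 0 | 31.4% | 19.3% |
| 0.3 | 30.8% | 19.0% |
| 0.5 | 29.8% | 18.3% |
| 0.7 | 28.4% | 17.4% |
| 0.9 | 26.6% | 16.2% |

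Check for the first row: 1 − (1 − 0.262)(1 − 0.071) = 0.314. For reference, four fully independent tests would give 1 − 0.84² × 0.96² = 35.0%, and the Bonferroni sum is 40%.

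**6. One direction only.** Rejections in favour of GDC-0032 use 8% and 2% in the upper tail, so the plan implies at most 10%. The ORR pair gives 13.1% and the pCR pair 3.5%. All four give 1 − (1 − 0.131)(1 − 0.035) = 16.1% if the endpoints are uncorrelated, and 15.0% at correlation 0.5.

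**7. Binary data.** Normal theory overstates the pCR part when events are rare. I simulated 60 + 60 mutant and 105 + 105 other patients, with a null ORR of 40%, pCR occurring only among responders, and a single-stratum Cochran-Mantel-Haenszel test.

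| Null pCR rate | ORR pair | pCR pair | All four | All four, continuity-corrected |
|---|---|---|---|---|
| 1% | 26.4% | 1.1% | 27.2% | 20.4% |
| 5% | 26.5% | 5.7% | 30.2% | 22.3% |
| 10% | 26.4% | 6.5% | 30.2% | 22.7% |

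The three middle columns use no continuity correction.

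**The case against.** **The SAP may supply the missing rule.** Testing order between nested populations is often left to the SAP, which was not available for this check. A fixed sequence would be compatible with testing each population at the full 16% or 4%. This is the strongest point, and it shows that the repair is easy. It does not rescue the present text, because Section 6.4.1 attributes the 20% to the two alpha values alone, and those values do not deliver it.

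**The family might be the two endpoints within one population.** On that reading 20% is correct. But Section 6.1 speaks of an overall rate, straight after naming both populations as test targets.

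**The figure depends on assumptions.** This stands in part. At the protocol's own 1% control pCR rate, the realised pCR error is below 4% and the total is 27.2%. The between-endpoint correlation is assumed. Neither brings the rate down to 20%, because the ORR pair alone is about 26%. A continuity-corrected test would give 20% to 23%, but the protocol names that correction only for the sample size, and incidental conservatism is not error control.

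**The 30% counts errors in both directions.** True, and the one-directional figure is 15% to 16%. The like-for-like comparison for that figure is 10%.

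**This is a phase II trial with a liberal alpha.** The sponsor may choose 20%. Having claimed control at that level, the procedure should provide it.

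**Conclusion.** The concern holds. As written, the four primary tests have a family-wise error rate of about 30%, not 20%. The nominal range is 26.6% to 31.4% for between-endpoint correlations from 0.9 down to 0, and 27.2% with binary data at a 1% null pCR rate.

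The result rests on the nesting correlation of 0.60, which follows from the protocol's own numbers, on the assumed range for the between-endpoint correlation, and on a Cochran-Mantel-Haenszel test without continuity correction. The conclusion that 20% is exceeded needs only the ORR pair, so it does not depend on the between-endpoint correlation or on how pCR behaves.

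**What to change.** Within each endpoint, use a fixed sequence. Test the PIK3CA mutant cohort first, at 16% for ORR or 4% for pCR. Test all enrolled patients at the same level only if the mutant result is significant. Each pair then carries at most 16% or 4%, and the total is at most 20%. The mutant cohort is the natural first step because it is the one the sample size was built on.

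The cost is wording in Sections 6.1 and 6.4.1 and in the synopsis. Mutant-cohort power is unchanged and no patients are added. The all-enrolled claim becomes conditional on the mutant result. The sponsor could reverse the order, and the mutant claim would then be the conditional one.

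Unconditional testing at reduced levels costs more:

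- Holding the ORR pair at 16% needs about 9.5% per test. Mutant-cohort ORR power then falls from 81% to 73% (continuity-corrected, 40:60 allocation).
- Halving alpha by population (8%, 8%, 2%, 2%) would need about 138 evaluable mutant patients for ORR and 145 for pCR, instead of 108 and 120.

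If both populations are to be tested unconditionally at the present levels, the family-wise error rate should be restated as about 30%.
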